Study Protocol and Statistical Analysis Plan

Study Title:

Comparative Evaluation of SmartMouth Clinical DDS Advanced Oral Rinse and Chlorhexidine Mouth Rinse

Date:

7-13-2015

Introduction:

The primary etiology for dental caries, gingivitis, and periodontal disease is the formation of bacterial colonies on the tooth surface. An inflammatory process follows the accumulation of dental plaque resulting in gingivitis. Many studies have demonstrated that plaque-induced gingivitis can be reversed following complete plaque removal. Patients are instructed by oral health professionals to regularly and thoroughly remove plaque using a daily oral hygiene regimen. Many patients demonstrate poor compliance, possibly due to lack of motivation, dexterity, or skill. An antimicrobial mouth rinse, when used as an adjunct to daily oral hygiene routine, can be beneficial to patients by reducing plaque accumulation and gingival inflammation.

Mouth rinses with 0.2% chlorhexidine gluconate are used commonly in Europe. Numerous studies have demonstrated the antiplaque and anti-gingivitis effectiveness of this rinse. Side effects associated with this mouth rinse include tooth staining, calculus formation, and altered taste sensation. Studies have also been conducted with 0.12% chlorhexidine. These trials found the antiplaque and anti-gingivitis effectiveness is comparable to the 0.2% solution, but with diminished side effects. The 0.12% chlorhexidine mouth rinse (Peridex®) is widely used on a prescription basis in the United States.

Clinical trials have confirmed the efficacy of cetylpyridinium chloride (CPC) mouthrinses, but there is limited data comparing CPC to other antimicrobial ingredients. CPC rinses are not associated with side effects such as staining or taste alteration, and its use is well tolerated by patients. SmartMouth Clinical DDS Advanced Oral Rinse (a.k.a. SmartMouth Advanced Clinical Formula) (Triumph Pharmaceuticals, Inc., St. Louis, MO) is an over-the-counter mouth rinse formulated to reduce plaque and gingivitis and to provide long term fresh breath through the elimination and prevention of bad breath sulfur gases (Volatile Sulfur Compounds or VSC) utilizing zinc-ion technology. The active ingredient in SmartMouth Clinical DDS Advanced Oral Rinse is 0.05% cetylpyridinium chloride (CPC).

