Supragingival calculus on the lingual surfaces of the six mandibular anterior teeth will be scored using the Volpe-Manhold calculus index (CI).³⁶ Supragingival calculus height in three defined planes on the lingual surface of each tooth will be measured using a periodontal probe. The measurements will be added and a mean subject score calculated.

Plaque will be scored based on the Turesky modification of the Quigley—Hein Plaque Index (PI).³³ A score of 0 – 5 will be assigned to six sites of each tooth (distobuccal, buccal, mesiobuccal, distolingual, lingual, mesiolingual) following the use of a disclosing solution. The Plaque Index for the entire mouth will be determined by dividing the total score by the number of surfaces examined.

Teeth with gross caries and third molars will not be scored. A complete periodontal examination will be performed for all subjects that meet the inclusion criteria. A panoramic radiograph will be taken for all subjects who do not have full mouth radiographs within the last year. Safety assessments will be made at each measurement visit.

Visit 2 will occur within four weeks of Visit 1. For this relatively small clinical study for which there are two centers and three treatments, subjects will be assigned treatments through the process of minimization to assure a balance in the number of subjects in each treatment group: Group 1 SM, Group 2 CHX or Group 3 PL. PL will be identical to SM, except it will not contain cetylpyridinium chloride, zinc chloride and sodium chlorite. Each group will consist of approximately 25 subjects. All subjects will be given a complete dental prophylaxis to remove plaque, calculus, and stain. Written and verbal oral hygiene instructions will be given that will includ a regular regimen of brushing twice daily and flossing daily. All subjects will be assigned a commercially available ADA accepted toothbrush and dental floss. They will be given a three-

week supply of the assigned mouth rinse with written and verbal instructions for use. Subjects will be instructed not to have their teeth professionally cleaned prior to study completion.

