The primary outcome measures are gingivitis and plaque. Secondary outcome measures are tooth discoloration, taste perception, malodor and calculus. For each outcome measure, a single value will be calculated for each subject—that is, the subject is the unit of measurement for analyses.

Analyses will be based on intention to treat (with randomized intervention). Sensitivity analyses will be based on as treated analyses. To test for differences among and between treatments, we will

use repeated measures analysis of variance (ANOVA) with treatment and location as the between-group factors and one within-subject (repeated-measures) factor with 2 levels: (1) measurements at visit 3 and (2) measurements at visit 4. For these analyses, we will use multivariate analysis of variance (MANOVA), which does not require the assumptions of compound symmetry (homogeneous pooled within-group variances and across-subjects covariances) and sphericity (orthogonal components). Post-hoc testing will be performed with the Tukey honestly significant difference ([HSD] test.

Sample-size calculation and power analysis (treatment effect of Smart Mouth ACF): One goal of the proposed study is to test the null hypothesis that the mean gingival score for Smart Mouth ACF is equal to the mean gingival score for the placebo (control). With alpha (the criterion for significance) set at 0.05, a 2-tailed test (which means that an effect in either direction will be interpreted), and a sample size of 20 and 20 for the two groups, the study will have a power of 99.9% to yield a statistically significant result. This computation is based on data from Ayad et al (2011), with the assumption that the mean difference is 0.44 (corresponding to means of 2.03 versus 1.59) and a common within-group standard deviation of 0.27 (based on SD estimates of 0.22 and 0.31). We assume that this effect size is reasonable, in the sense that an effect of this magnitude is anticipated in this field of research. We could report an observed difference of 0.44 with a 95.0% confidence interval of 0.27 to 0.61. Based on plaque scores given in Ayad et al (2011) and a sample size of 20 in each group, we would have a power >99.9% to demonstrate a treatment effect for Smart Mouth ACF. Our intent is to enroll 25 subjects into each group. Our sample-size calculations assume a 20% dropout rate. We, however, anticipate that the dropout rate will be less than 10%.

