Equivalence of Smart Mouth ACF with 0.12% chlorhexidine. We will have power of 82% to demonstrate that the mean gingivitis score for Smart Mouth ACF is the same (neither lower nor higher) than the mean for .12% chlorhexidine. This assumes that the mean values for the two treatments are equal, with a common within-group standard deviation of 0.25, that a difference of .20 points or less is unimportant, that the sample size in the two groups will be 21 and 21, and that alpha (1 tailed) is set at .05. For this calculation, we used standard deviations from Ayad et al (2011). Formally, the null hypothesis is that the mean for Smart Mouth ACF is 0.20 points lower or higher than the mean for .12% chlorhexidine, and the study has power of 81.7% to reject this null. Equivalently, the likelihood is 81.7% that the 95.0% confidence interval for the mean difference will exclude a difference of 0.20 points in either direction.

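### The SM-CHX equivalence conclusion for gingivitis is not tied to either rinse beating placebo, so it could stand without evidence that the trial can detect a rinse effect

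*Combined protocol and SAP*

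**What the plan says.** The equivalence paragraph of Data Analysis concerns the mean gingivitis score for SM and CHX. Its premises are "This assumes that the mean values for the two treatments are equal" and "that a difference of .20 points or less is unimportant". Its null hypothesis is a difference of 0.20 in either direction, rejected when the confidence interval excludes 0.20 on both sides. Placebo does not appear in that paragraph.

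Placebo appears earlier in Data Analysis, in two places. The sample-size paragraph sets a superiority aim: "One goal of the proposed study is to test the null hypothesis that the mean gingival score for Smart Mouth ACF is equal to the" placebo mean. The analysis paragraph plans a three-treatment repeated-measures ANOVA with Tukey HSD post hoc, which covers SM-PL, CHX-PL and SM-CHX. No hypothesis or power is stated for CHX against PL. No testing order is given, and no text makes the equivalence conclusion depend on a placebo comparison.

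Materials and Methods describes visit 2, when the rinse is dispensed: "All subjects will be given a complete dental prophylaxis to remove plaque, calculus, and stain". Hygiene instruction, a toothbrush and floss are given at the same visit. Outcomes are analysed at visits 3 and 4, three and six weeks later. The Introduction states: "Many studies have demonstrated that plaque-induced gingivitis can be reversed following complete plaque removal".

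**The concern.** Two rinses can give similar means because both work or because neither adds much to what every subject received. The SM-CHX difference cannot tell these apart; the comparison with placebo can. Here the second explanation is plausible on the protocol's own account, since all arms start from a full prophylaxis and the Introduction says plaque removal can reverse the condition being scored.

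If that shared treatment leaves little for a rinse to add over six weeks, a small SM-CHX difference is what an inert rinse would show too. The less the rinses add, the easier equivalence becomes. The trial has the placebo arm that would reveal this, but the equivalence paragraph does not use it. At stake is a statement that an over-the-counter rinse is equivalent to 0.12% chlorhexidine, made from a trial that may not have separated either rinse from placebo.

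**Working it through.** **Inputs from the equivalence paragraph.** Margin 0.20; SD: "with a common within-group standard deviation of 0.25"; size: "that the sample size in the two groups will be 21 and 21"; level: "alpha (1 tailed) is set at .05". The sample-size paragraph gives an assumed SM-PL difference of 0.44.

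**Assumptions of this check.** PL also has 21 subjects. There is one time point, normal data and a pooled variance on 3 × 21 − 3 = 60 df; the location factor is ignored. The true CHX-PL effect is varied from 0 to 0.44, because the documents give no figure for it after prophylaxis.

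**1. The plan's own figure.** SE = 0.25 × √(2/21) = 0.0772. Noncentrality = 0.20/0.0772 = 2.592. One one-sided t test at 0.05 with 40 df (critical value 1.684) has power 81.7%, which matches the plan. Rejecting on both sides, as equivalence requires, gives 2 × 0.8168 − 1 = 63.4% with 40 df, or 64.1% with 60 df. The calculations below use both sides. This power depends only on the SM-CHX difference, so it is the same whether both rinses work by 0.44 or by nothing.

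**2. The criterion in GI points.** A one-tailed 0.05 level corresponds to a 90% CI inside ±0.20. With 60 df, the observed difference must be smaller than about 0.20 − 1.671 × 0.0772 = 0.071.

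**3. Chance of concluding equivalence with SM inert (equal to PL).** If CHX adds δ, this is approximately Φ((0.071 − δ)/0.0772) − Φ((−0.071 − δ)/0.0772). For δ = 0 it is 2Φ(0.92) − 1 = 0.64. For δ = 0.10 it is Φ(−0.37) − Φ(−2.22) = 0.34. A three-arm simulation (1,000,000 runs per row) gives:

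| True CHX-PL | 90% CI, no condition | 95% CI, no condition | 90% CI, and both rinses beat PL by Tukey |
|---|---|---|---|
| 0 | 64.2% | 44.5% | 0.1% |
| 0.05 | 54.9% | 37.1% | 0.3% |
| 0.10 | 34.4% | 21.6% | 0.5% |
| 0.15 | 15.5% | 8.7% | 0.5% |
| 0.20 | 5.0% | 2.4% | 0.3% |
| 0.44 | 0.0% | 0.0% | 0.0% |

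The 95% column is shown because the equivalence paragraph also speaks of a 95% interval. The Tukey critical value for three groups and 60 df is 2.403 on the t scale, so a rinse must beat PL by about 2.403 × 0.0772 = 0.185.

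**4. Cost of the condition when both rinses work equally (90% CI).**

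| True effect of each rinse over PL | No condition | Both beat PL, Tukey | Both beat PL, unadjusted two-sided 0.05 |
|---|---|---|---|
| 0.15 | 64% | 15% | 25% |
| 0.20 | 64% | 32% | 43% |
| 0.30 | 64% | 59.5% | 62% |
| 0.44 | 64% | 64% | 64% |

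**The case against.** Four objections carry weight.

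- **The placebo comparisons are already planned.** This stands. Tukey HSD covers SM-PL and CHX-PL, and SM-PL is a stated goal. With SM inert and CHX adding 0 to 0.15, equivalence together with a significant SM-PL win (unadjusted two-sided 0.05) occurs at most 1.8% of the time. A reader who looks at both results would rarely be misled. What is missing is the rule that they be read together.
- **The equivalence paragraph is a power statement, not a rule for claims.** This is partly right. But it states the null and the interval that rejects it, and nothing else in the documents says when equivalence may be concluded.
- **The risk needs small effects.** This stands. At 0.44 it is nil, and the Introduction cites numerous studies of chlorhexidine's effectiveness. Past efficacy does not, however, show that this trial, with prophylaxis for everyone, can detect it.
- **The condition costs power.** This also stands; the second table shows how much.

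Three stronger readings are tempting, and the documents do not support them. A reader might infer that the plan never compares the rinses with placebo; the three-treatment ANOVA does. A reader might infer that prophylaxis will erase the differences; the documents say only that plaque removal can reverse gingivitis and give no residual difference at three or six weeks. A reader might call the 64% a type I error. It is not: where the true SM-CHX difference is below 0.20, the rinses are equivalent by the plan's own margin. At exactly 0.20 the rate is 5%, the nominal level.

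**Conclusion.** The point holds as a missing condition for assay sensitivity. Equivalence on gingivitis rests on the SM-CHX difference alone, and the planned placebo comparisons are not linked to it. With an inert SM, the chance of concluding equivalence runs from 64% when CHX adds nothing, through 34% at 0.10, to 5% at 0.20 and 0% at 0.44. These figures rest on SD 0.25, 21 per arm, a 90% CI and an assumed range of CHX effects. With 25 per arm and all arms equal, the chance rises to 74.7% (two-arm test, 48 df).

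How likely the small-effect scenarios are cannot be judged from the documents. The gap is in the decision rule, not in the design or the data to be collected, and it should be closed before the analysis.

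**What to change.** Add to the equivalence paragraph: SM will be called equivalent to CHX for gingivitis only if, in the same repeated-measures model and at one time point named in advance (visit 3, visit 4, or the average of the two), both CHX and SM are significantly better than PL by the planned Tukey HSD test. Otherwise, report the SM-CHX difference with its confidence interval and make no equivalence claim.

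The time point must be fixed because the plan names neither follow-up visit as primary. Once it is fixed, no extra alpha is needed: the placebo conditions must hold in addition to the equivalence test, so they can only make the claim harder to reach.

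The change needs no new subjects, visits or measurements. Its price is a smaller chance of claiming equivalence when true effects are modest: from 64% to about 59.5% at 0.30, 32% at 0.20 and 15% at 0.15, with no loss at 0.44. Unadjusted tests for the condition would cost less (62, 43 and 25%), but would depart from the plan's Tukey procedure and would have to be specified as such.

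### The 81.7% equivalence power is the power of a single one-sided test; the two-sided equivalence claim has about 63% power on the plan's own inputs, and about 43% under its 95% interval wording

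*Combined protocol and SAP*

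**What the plan says.** The last paragraph of the Data Analysis section, on equivalence with 0.12% chlorhexidine, describes a two-directional aim. The study is to show that "the mean gingivitis score for Smart Mouth ACF is the same (neither lower nor higher) than the mean for .12% chlorhexidine". The formal statement is that "the null hypothesis is that the mean for Smart Mouth ACF is 0.20 points lower or higher than the mean for .12% chlorhexidine". The margin rests on the judgement "that a difference of .20 points or less is unimportant".

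The inputs to the calculation are a common SD of 0.25, "the sample size in the two groups will be 21 and 21, and that alpha (1 tailed) is set at .05", and equal true means ("This assumes that the mean values for the two treatments are equal").

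The plan then states the result twice. First, "the study has power of 81.7% to reject this null", given as 82% at the start of the paragraph. Second, as an equivalent statement, "the likelihood is 81.7% that the 95.0% confidence interval for the mean difference will exclude a difference of 0.20 points in either direction".

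The preceding paragraph plans 25 subjects per group and says "Our sample-size calculations assume a 20% dropout rate", while expecting dropout below 10%.

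**The concern.** Rejecting a null hypothesis that the difference is 0.20 or more in either direction takes two rejections: the difference must be shown to exceed −0.20 and also to be below +0.20. When the true difference is zero, each test can fail on its own, so the probability of passing both is clearly lower than the probability of passing one. A power close to 82% with 21 per group is what one would expect from a single one-sided test.

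The second statement of the result does not fit the first. Two one-sided tests at 0.05 correspond to a 90% confidence interval lying inside the margin. A 95% interval is wider and is a stricter criterion, so the two cannot have the same power. The same data could also pass one criterion and fail the other.

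The comparison with chlorhexidine is in the study title and the stated aim, gingivitis is a primary outcome, and this paragraph is the only power statement for that comparison. If the figure is wrong, the plan understates the chance of an inconclusive result when the rinses are in fact the same. There is then a risk that such a result is taken as evidence of a difference.

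**Working it through.** **Inputs**, all from the equivalence paragraph: true difference 0, margin Δ = 0.20, SD σ = 0.25, n = 21 per group, one-tailed α = 0.05.

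**Common quantities.**
- Standard error: SE = σ√(2/n) = 0.25 × √(2/21) = 0.0772
- Degrees of freedom: 2n − 2 = 40
- Noncentrality: Δ/SE = 0.20/0.0772 = 2.592
- Critical values with 40 df: 1.684 (α = 0.05) and 2.021 (α = 0.025)

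**Step 1: reproduce the plan's figure.** The power of one one-sided t-test against one limit is P(T > 1.684), where T is noncentral t with 40 df and noncentrality 2.592. The result is 81.68%, which is the plan's 81.7%.

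**Step 2: require both limits at α = 0.05 each.** Equivalence is shown when |d| + 1.684·s < 0.20, where d is the observed difference and s its estimated standard error; that is, when the 90% interval lies inside ±0.20. With a true difference of 0, the power is the average of 2Φ((0.20 − 1.684·s)/SE) − 1 over the distribution of s (s²/SE² distributed as chi-square with 40 df, divided by 40), counted as zero where 1.684·s exceeds 0.20. The result is 63.4%.

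A hand check agrees. Each limit is missed with probability 1 − 0.8168 = 0.1832, so both are passed with probability of about 1 − 2 × 0.1832 = 0.634.

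**Step 3: the 95% interval wording.** The same calculation with 2.021 in place of 1.684 gives 43.1%.

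**Step 4: simulation.** With 400,000 simulated trials on the same inputs, one limit was passed in 81.7%, both limits at 0.05 in 63.4%, and the 95% interval criterion in 43.2%.

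**Step 5: other sample sizes, SD 0.25.**

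| Evaluable per group | Where it comes from | Both limits, 90% interval | 95% interval inside ±0.20 |
|---|---|---|---|
| 20 | 25 × (1 − 0.20) | 59.9% | 38.8% |
| 21 | equivalence paragraph | 63.4% | 43.1% |
| 23 | 25 with dropout just under 10% | 69.5% | 51.2% |
| 25 | no dropout | 74.7% | 58.3% |

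As a sensitivity check, the SD of 0.27 from the placebo calculation gives 52.5% and 30.1% at 21 per group.

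**Step 6: sample size that would support the stated power.** At SD 0.25, 81.7% needs 29 evaluable per group under the 90% interval rule and 35 under the 95% rule. For 80% the numbers are 28 and 34.

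**The case against.** The case against accepts the arithmetic and disputes the surrounding points.

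- **The figure of 21.** Set against 25 per group less 20%, 21 looks like a mismatch, but Materials and Methods plans 80 subjects in three groups: 80/3 = 26.7, and 26.7 × 0.8 = 21.3. So 21 can be derived from the documents. This stands. The n = 20 row follows from the sample-size paragraph, but the finding does not depend on it.
- **Retention.** The plan expects less than 10% dropout, and at 23 per group the 95% interval criterion has 51.2% power, slightly above one half. This also stands. Power under both criteria nevertheless remains below 81.7% even with all 25 retained.
- **The SD of 0.27.** It belongs to the placebo comparison and may not apply here. That is fair; it is shown only as a sensitivity check.
- **The planned analysis.** The trial will use a repeated-measures model over visits 3 and 4 with location as a factor, so precision may differ from a simple two-sample t-test. The documents give no within-subject correlation, so actual power is unknown. The figures here correct the plan's own calculation and do not forecast the result.
- **Deleting the interval sentence.** The analysis text specifies only difference tests and Tukey comparisons, so this sentence is the nearest thing to an equivalence decision rule. That is a reason for the replacement text to name the rule, which the fix below does.
- **Consequences.** A wrong power figure does not inflate type I error or invalidate an equivalence claim that is met, and how a failed result would be read is conjecture. Both are true, but the stated power remains wrong.

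Reading 95.0% charitably as a one-sided bound gives the 63% figure. No two-directional reading gives 81.7%.

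**Conclusion.** The concern holds. The plan reports the power of a one-directional non-inferiority test as the power of a two-directional equivalence test. The overstatement is 81.7 − 63.4 = 18.3 percentage points for TOST at one-tailed 0.05, and 81.7 − 43.1 = 38.6 points under the 95% interval wording. The risk of missing equivalence when the rinses are identical is 36.6% or 56.9%, against the 18.3% implied. These figures assume normally distributed scores, a two-sample t-test, a true difference of exactly zero, SD 0.25 and 21 per group; any true difference other than zero would lower them. The superiority calculation against placebo is not affected. The point must be fixed because it misstates the only power given for the chlorhexidine comparison on a primary outcome.

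**What to change.** In the equivalence paragraph, replace both the 82% and the 81.7% with about 63%. State the rule behind the new figure: two one-sided tests at 0.05 each, equivalently a 90% confidence interval inside ±0.20, with 21 evaluable per group and SD 0.25. Add that power is about 60% with 20 per group. Delete the sentence that equates this power with a 95% interval. Because the replacement names the test and the interval, the plan still has a stated equivalence criterion.

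If the intended question is only whether SmartMouth is worse than chlorhexidine by more than 0.20, call it non-inferiority, remove the two-directional wording, and keep 81.7% at 21 per group.

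The cost is a change of wording and number in one paragraph, with a less favourable stated power. No extra enrolment or design change is proposed.

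### The 81.7% equivalence power against chlorhexidine is a one-direction figure; two-direction power is about 63% or 43%, depending on which of two conflicting interval rules is meant

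*Combined protocol and SAP*

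**What the plan says.** The paragraph on equivalence with 0.12% chlorhexidine, at the end of Data Analysis, makes a two-direction claim about SmartMouth relative to chlorhexidine: "We will have power of 82% to demonstrate that the mean gingivitis score for Smart Mouth ACF is the same (neither lower nor higher". Its inputs are equal true means, a common SD of 0.25, a margin of 0.20 points, 21 subjects in each group, and "alpha (1 tailed) is set at .05". The null hypothesis is a difference of 0.20 either way, and "the study has power of 81.7% to reject this null". The paragraph then restates this as an interval criterion: "Equivalently, the likelihood is 81.7% that the 95.0% confidence interval for the mean difference will exclude a difference of 0.20 points in either direction".

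The analysis methods earlier under Data Analysis have a different purpose. The repeated-measures ANOVA/MANOVA on visits 3 and 4 is there "To test for differences among and between treatments", and "Post-hoc testing will be performed with the Tukey honestly significant difference" test. They mention no margin and no equivalence interval.

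The sample-size paragraph for the placebo comparison bears on two points. It uses the term 95.0% confidence interval with figures attached: "We could report an observed difference of 0.44 with a 95.0% confidence interval of 0.27 to 0.61". It also gives the attrition basis: "Our sample-size calculations assume a 20% dropout rate", with 25 to be enrolled per group and dropout below 10% anticipated.

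**The concern.** Three things do not fit together.

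1. Testing against both margins at one-tailed 0.05 is the two one-sided tests procedure, which is the same as requiring a 90% interval to lie within -0.20 to +0.20. Requiring a 95% interval to do so is a stricter rule, yet the plan presents the two as interchangeable.
2. A single power figure is attached to both rules, and for a two-direction claim at this sample size it looks too high.
3. The margin appears only in a power statement. The pairwise procedure actually planned is a difference test, and a non-significant Tukey comparison does not establish equivalence.

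Comparison with chlorhexidine is part of the trial's stated aim, and gingivitis is a primary outcome. If the rule is not settled beforehand, some results will be equivalent under one reading and not under the other. A failure to show equivalence would also be misjudged by anyone who believed the study had 82% power to show it.

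**Working it through.** **Inputs** (equivalence paragraph): n = 21 per group, SD = 0.25, margin = 0.20, true difference = 0, one-tailed alpha = 0.05. From these:

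- SE = 0.25 × √(2/21) = 0.0772, df = 40
- margin/SE = 0.20/0.0772 = 2.59
- t(0.95, 40) = 1.684; t(0.975, 40) = 2.021

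**Step 1: reproduce the plan's figure.** The power of one one-sided t-test against one margin is P(T > 1.684), where T is noncentral t with 40 df and noncentrality 2.59. The result is 0.8168, which matches the stated 81.7%. The figure is therefore the power to exclude 0.20 in a single direction.

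**Step 2: power in both directions.** Equivalence requires |observed difference| + t × (estimated SE) < 0.20. With a true difference of 0, each side fails equally often, and both sides almost never fail together, so power ≈ 1 − 2 × (1 − one-direction power).

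| Rule | One direction | Both directions |
|---|---|---|
| 0.05 per side (90% interval) | 81.68% | 1 − 2 × 0.1832 = 63.4% |
| 0.025 per side (95% interval) | 71.56% | 1 − 2 × 0.2844 = 43.1% |

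Exact integration over the sample SD gives 63.4% and 43.1%; a simulation of 400,000 trials gives 63.4% and 43.2%.

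**Step 3: what the plan means by a 95.0% interval.** In the placebo paragraph (difference 0.44, SD 0.27, 20 per group) the SE is 0.27 × √(2/20) = 0.0854.

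- Two-sided 95%: 0.44 ± 2.024 × 0.0854 = 0.267 to 0.613, which is the printed 0.27 to 0.61.
- 90%: 0.44 ± 1.686 × 0.0854 = 0.296 to 0.584, which is not.

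The term is two-sided in this document. Reading it in the equivalence paragraph as a pair of one-sided 95% bounds would remove the conflict between the rules, but power would still be 63.4%.

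**Step 4: where the two rules disagree.** When the sample SD is 0.25, the largest observed difference that passes is:

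- 90% interval: 0.20 − 1.684 × 0.0772 = 0.070
- 95% interval: 0.20 − 2.021 × 0.0772 = 0.044

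Differences between about 0.044 and 0.070 pass the first rule and fail the second. With a true difference of 0, the rules disagree in 63.4% − 43.1% ≈ 20% of trials. At a true difference of 0.20, false equivalence is 5.0% and 2.4% respectively.

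**Step 5: other sample sizes** (SD 0.25, single time point).

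| Evaluable per group | Basis | 90% interval | 95% interval |
|---|---|---|---|
| 20 | 25 less 20% dropout | 59.9% | 38.8% |
| 21 | as stated | 63.4% | 43.1% |
| 23 | dropout under 10% | 69.5% | 51.2% |
| 25 | no dropout | 74.7% | 58.3% |

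The smallest n reaching 81.7% is 29 (82.8%) with the 90% interval and 35 (81.9%) with the 95% interval. Allowing for 20% dropout, 29/0.8 and 35/0.8 round up to 37 and 44 enrolled per group.

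**Step 6: averaging visits 3 and 4.** The SD becomes 0.25 × √((1 + r)/2), where r is the within-subject correlation. The documents do not give r, so the values below are assumptions. At 21 per group:

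| r | 90% interval | 95% interval |
|---|---|---|
| 0.5 | 80.5% | 66.3% |
| 0.7 | 73.7% | 56.7% |
| 0.9 | 66.8% | 47.5% |

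**The case against.** The strongest reply concerns the analysed contrast. The planned model has visits 3 and 4 as a repeated factor, and its treatment main effect is naturally the two-visit average, which is more precise than one visit. With 23 evaluable per group, the 90% rule then gives about 85% power at r = 0.5 and 79% at r = 0.7, close to the claim. This stands as a reason to state the contrast and to treat 63% as the power for the stated inputs, not necessarily for the planned model. It does not rescue the printed figure: that paragraph describes a simple two-group comparison of 21 and 21 with SD 0.25, claims no gain from averaging, and its 81.7% is reproduced exactly by a one-direction test.

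Second, the margin, the null and an interval criterion all sit under the same Data Analysis heading as the ANOVA, and the plan nowhere says that a non-significant Tukey result will be read as equivalence. That is fair. What remains is narrower: the criterion is worded as a power statement and is not tied to the fitted model, to a visit or average, or to the Tukey adjustment.

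Third, the only interval rule written down is the 95.0% one, so a reader could simply apply it. That would settle the rule on its stricter form, but the power would then be about 43%, and the stated one-tailed alpha of 0.05 would be wrong.

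Finally, neither rule lets false equivalence exceed 5%, and the test against placebo is untouched. Both are true. They limit the harm to an ambiguous verdict and a wrong power figure.

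**Conclusion.** The concern holds. The stated power is wrong for the claim it supports: it is overstated by about 18 percentage points (81.7% against 63.4%) if one-tailed 0.05 governs, and by about 39 points (81.7% against 43.1%) if the 95% interval governs. The two rules are not equivalent, and the analysis methods do not say which applies or to which visit. These sizes assume 21 evaluable per group, SD 0.25 for the analysed contrast, a true difference of exactly 0 and a two-sample t analysis. Averaging visits would raise the power by an amount that depends on a correlation the plan does not give. Because the comparison concerns a primary outcome and is part of the stated aim, this should be corrected before the data are analysed.

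**What to change.** In the analysis methods, add one rule for SmartMouth versus chlorhexidine on the gingival index. For example: equivalence is declared only if the 90% confidence interval for the mean difference at visit 4 from the fitted model (two one-sided tests at 0.05, not Tukey-adjusted) lies wholly within -0.20 to +0.20; Tukey HSD applies only to the difference tests. The average of visits 3 and 4 could be named instead, but only one contrast should be chosen, and in advance.

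In the equivalence paragraph, do one of the following:

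- change 95.0% to 90%, and replace both 82% and 81.7% with about 63%; or
- keep the 95% interval, set alpha to one-tailed 0.025, and restate the power as about 43%.

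State the assumptions beside the figure (21 per group, SD 0.25 for the analysed contrast, true difference 0). If visits are averaged, recompute the power and state the assumed correlation. It would also help to interpret any equivalence finding alongside the chlorhexidine versus placebo result; this is advice, not a required change.

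The cost is a few sentences and one extra interval from a model already planned. The drawback is a less favourable power statement. Enrolling more is optional: keeping about 82% with a single-visit SD of 0.25 and 20% dropout would take about 37 (90% interval) or 44 (95% interval) per group instead of 25.
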